6. The blind will be broken at the end of the 8 week study period. Remitters (HRSD < 11) will be continued on the same medication. Responders to placebo will be followed off of medication. Placebo non-responders

will be treated openly with escitalopram [or duloxetine], while escitalopram [or duloxetine] non-responders will be treated as clinically indicated with augmentation or switch in class of antidepressants.

You can upload charts or diagrams if any

Criteria for Early Discontinuation

Criteria for Early Discontinuation

If a patient discontinues medication due to tolerability problems, ineffectiveness, patient preference, or other reasons, the patient will be dropped out of the study and enter the 3 month long open treatment phase. Appropriate medication options will be discussed with the patient based on their symptoms and history. If the patient wishes, they will be provided referrals for psychotherapy or treatment options outside of our research clinic. No further research measures will be conducted once a patient enters the open treatment phase.

Patients in all treatment cells will be discontinued from the acute treatment phase if there is there is a rating of 6 (much worse) or 7 (very much worse) on the CGI—I for 2 consecutive weeks. Patients may also be discontinued from the study if this is indicated in the clinical judgement of the study physician and/or principal investigator. Patients receiving escitalopram/duloxetine may continue receiving the same medication if clinically indicated after being dropped from the study. No further research measures will be performed on patient dropped from the study.

Patients will be informed that should they experience a crisis or acute symptom worsening between scheduled weekly appointments, they should call their study clinician via the clinic office/research coordinator or the 24 hr doctor on call pager for the LLDC. The study physician will evaluate the patient and make appropriate follow up arrangements, which may include activating EMS, calling the relevant mobile crisis team, or scheduling pt for immediate outpatient appointment in the LLDC. Patients in crisis will be assessed immediately and appropriate clinical action taken as above (i.e., those meeting criteria for early discontinuation will be dropped from the study and treated openly).

Blood and other Biological Samples

CBC, blood chemistries, and electrolytes will be drawn before initiating escitalopram/duloxetine or placebo. The total amount of blood drawn should be no greater than 20cc.

Assessment Instruments

Clinical measures

1. SCID IV -- 30 minutes
2. HRSD --15 minutes
3. QIDS -- SR 10 minutes
4. CES -- 5 minutes
5. CGI-I -- 1 minute
6. Blind assessment -- Patient guess -- 1 minute
7. Blind assessment -- Doctor guess -- 1 minute
8. TESS -- 3 minutes
9. ATHF -- 5 minutes
10. Credibility and Expectancy Scale -- 5 minute
11. HARS -- 15 minutes
12. UCLA Revised Loneliness Scale -- SR -- 1 minute

Neuropsychological tests

1. Wechsler Test of Adult Reading (WTAR)--5 min
2. Mini Mental State Examination (MMSE) -- 8 min
3. Stroop Color Word Test (Stroop) -- 5 min
4. Mattis DRS- I/P subset -- 10 min
5. Digit Symbol Subtest of the WAIS III -- 2 min
6. Logical Memory Test (WMS III) -- 10min

Please attach copies, unless standard instruments are used

Off label and investigational use of drugs/devices

Choose from the following that will be applicable to your study

Research Related Delay to Treatment

Will research procedures result in a delay to treatment?

Yes

Maximum duration of delay to any treatment

It is possible that treatment may be delayed due to scheduling study MRI scans and neuropsychological testing, though we will make every effort not to delay treatment. If there are scheduling difficulties, treatment will not be delayed more than 1 week.

Maximum duration of delay to standard care or treatment of known efficacy

There will also be a delay of 8 weeks for 10/130 of patients (those assigned to receive placebo).

Justification: In this study 10 subjects will be randomized to placebo in place of antidepressant treatment with escitalopram/duloxetine, which is not so toxic that patients routinely refuse treatment. The use of placebo rather than escitalopram/duloxetine could result in longer exposure to depressive symptoms, so the

IRB algorithm would seem to judge the risk of placebo as high. This risk is mitigated since there are not large differences between antidepressant medications and placebos in most clinical trials. Typical antidepressant response rates in placebo controlled trials are 40-45%, while placebo response rates are 30-35%. If 10 subjects in this study are assigned to placebo rather than escitalopram/duloxetine, then based on these estimated rates only 1 subject would fail to respond to placebo who may have responded to escitalopram/duloxetine. That being said, continuing with the IRB algorithm, it is not possible to accurately predict placebo response in a single study (placebo response ranged widely between 13-52% in the Walsh et al 2002 meta-analysis). Finally, the potential benefit of understanding the cognitive and neural pathways by which placebo and expectancy effects cause improvement in depressive symptoms is substantial. Therefore, according to the algorithm provided by the IRB, the use of placebo in this study is ethical.

Treatment to be provided at the end of the study

At the end of the acute treatment protocol, appropriate treatment (medication continuation, change in medication, and/or follow-up) will be provided free for 3 months. Subjects will receive 3 months of free doctor visits in the clinic and at least 1 month of free medication. Every effort will be made to provide free medication for 3 months total, but we cannot guarantee the availability of free medication beyond 1 month. At the end of the three month period, patients will be referred out for further psychiatric follow up.

Clinical Treatment Alternatives

Clinical treatment alternatives

The alternative to participating in this study is to seek treatment outside the research project. Patients who would rather receive treatment elsewhere will be given referrals to appropriate and affordable care.

Risks/Discomforts/Inconveniences

Risks that could be encountered during the study period

The main risks in this study are (1) patients may not respond to the medication treatment, (2) patients assigned to placebo may experience continued symptoms or clinical worsening, (3) side effects of the medication, (4) risks related to MRI, and (5) specific risks associated with being a participant aged over 60 years (such as having a comorbid medical condition, or being cognitively impaired). There are also minimal risks associated with the blood draws, but there is no greater risk in this protocol for this procedure than in any standard clinical setting.

Describe procedures for minimizing risks

Regarding (1), treatment with SSRIs and SNRIs are accepted first line treatments for depression. Reliable evidence does not exist for the superiority of another medication or psychotherapy to escitalopram in depressed patients. Patients will be seen weekly to have their symptoms assessed, and patients who exhibit clinical worsening (as described in above procedures) will be dropped from the study and receive clinical treatment. Regarding (2), it is the case that patients in the Placebo Controlled Group will not receive a proven effective treatment for their condition if they are assigned to placebo. However, the risk of permanent harm to subjects will be minimized by restricting the study to depressed, nonsuicidal patients, following them closely, and dropping them from the study for signs of clinical deterioration. Regarding (3), commonly observed side effects associated with escitalopram and duloxetine are diaphoresis, diarrhea, nausea, insomnia, somnolence, disorder of ejaculation, impotence, and fatigue. The FDA has also placed a

black box warning in the package insert for all SSRIs warning of increased suicidal ideation and behavior. Side effects of the medication will be assessed at each visit. If the side effects represent an intolerable burden in the assessment of the patient or the treating clinician, the medication will be discontinued. Regarding (4), the Magnetic Resonance (MR) scanner uses strong magnetic fields and radio waves to take measurements in the brain. MRI involves lying on a table that slides into a large magnet shaped like a cylinder. Before beginning the procedure, we will determine that patients do not have a pacemaker or any unsafe metallic implants such as an aneurysm clip or heart valve and certain tattoos, and they will be asked to remove any metal or magnetized objects (such as keys, chains, jewelry, retainers, medication patches, hairpins or credit cards). They will be asked to lie flat on the back in the MRI scanner for approximately 90 minutes and to remain as still as possible. Some people have reported sensations during MRI scans, such as "tingling" or "twitching" (or, very rarely, a painful sensation), which are caused by changes in the magnetic field that can stimulate nerves in the body. With any MRI scan, on occasion, some people experience nervousness or types of metallic implants, and medication patches, we are not aware of any other potentially dangerous interactions or hazards associated with the MRI scan. The MRI scanner also produces a loud noise; earplugs will be provided to reduce this discomfort. If a patient experience any discomfort and wish to stop the scan, he/she can tell the MRI technologist who will stop the scan immediately. In our experience, no one has had sensations from the MRI that did not stop when the scanning stopped. Finally, we will mitigate the risks associated with increased medical problems in older adults by doing a careful physical examination and blood tests to detect an unstable, severe, or acute medical problem. Since cognitive impairment is a condition impacting older adults, we will measure a MMSE and exclude subjects with a score lower than 24.

Methods to Protect Confidentiality

Describe methods to protect confidentiality

All records of the participating subjects will be kept in a locked room with access provided only to staff members. Patients' names will be linked with code numbers in a password protected file to which only the research assistant has access. Only these code numbers will appear on all pill bottles and paper measures collected during study. All data collected will be kept confidential and used for professional purposes only. Publications using these data will be done in a manner that protects the subjects' anonymity. All electronically stored data will be accessible by password known only to the principal investigator and research assistants for the study. All MRI scans and related data will be kept on the secure, password protected, MRI server. MRI scan reports will be provided to the clinic by the MRI scanner, and kept in a locked file.

Will the study be conducted under a certificate of confidentiality?

No

Direct Benefits to Subjects

Direct Benefits to Subjects

Patients who are not currently in treatment and are experiencing depressive symptoms may receive a medication proven effective for their condition. Therefore, the major benefit is that patients will achieve

remission from the depression as a result of participating in the study.

Compensation and/or Reimbursement

Will compensation or reimbursement for expenses be offered to subjects?

Yes

Please describe and indicate total amount and schedule of payment(s).

Include justification for compensation amounts and indicate if there are bonus payments.

Subjects will receive reasonable reimbursement for transportation related costs associated with study involvement as long as they provide receipts. Reimbursement is limited to no more than \$10 per week. To compensate subjects for the time required for the MRI scan, subjects will be compensated \$100 for the scan.

References

References

NIH Consensus Conference. Diagnosis and treatment of depression in late life. JAMA 1992; 268:1018–1024.

Alexopoulos GS. Role of executive dysfunction in late-life depression. J Clin Psychiatry 2003; 64:18-23.

Uploads

Upload the entire grant application(s)

[name].pdf

Upload copy(ies) of unbolded Consent Form(s)

6838_CF_English_7.23.18_UNCHANGED_2019.pdf

6838_CF_Spanish_7.31.18_UNCHANGED_2019.pdf

Upload copy(ies) of bolded Consent Form(s)

Upload copy(ies) of recruitment materials/ads to be reviewed

Upload copy(ies) of the HIPAA form

6836_HIPAA_English_7.31.18.pdf

6836_HIPAA_Spanish_July2018.pdf

Upload any additional documents that may be related to this study

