Specific Aim 1: To determine whether ED and/or WMH moderate the difference in patient expectancy and antidepressant outcome between the open vs. placebo-controlled conditions. Hypothesis 1: Greater ED and WMH will be associated with smaller differences in expectancy and antidepressant outcome between conditions.

Specific Aim 2: To determine whether a loss of expectancy effects mediates the relationship between ED/WMH and poor antidepressant outcome. Hypothesis 2: ED and WMH will be associated with decreased change in depressive symptoms, and these associations will be mediated by a decreased contribution of expectancy to antidepressant outcome.

Exploratory Aim: To assess the integrity of frontostriatal and frontolimbic white matter tracts using DTI and explore whether specific damage to these pathways is associated with diminished expectancy effects in patients with LLD.

Substantiating this model would provide a mechanism explaining how ED and WMH predict non-response to antidepressant medications in LLD. Understanding the mechanisms of antidepressant non-response in LLD has the potential to yield treatments based on specific and rational designs that target the involved biological pathways. By combining inexpensive and widely available antidepressant medications with psychoeducational interventions or targeted psychotherapies to enhance expectancy, it may be possible to significantly improve antidepressant response rates in LLD patients.

Description of Subject Population

Sample #1

Specify subject population

N=130 outpatients with MDD

Number of completers required to accomplish study aims

90

Projected number of subjects who will be enrolled to obtain required number of completers

130

Age range of subject population

60-90

Gender, Racial and Ethnic Breakdown

Gender: We anticipate the sample will be composed of approximately 60% women and 40% men.

Racial/ethnic group: On the basis of previous depression studies conducted in the Adult and Late Life Depression Clinic, it is anticipated that the sample will be composed of approximately 75% Caucasian, 15% African American, and 10% Hispanic subjects.

Description of subject population

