The proposed study will enroll 130 outpatients who are (1) men and women aged 60-90 years, (2) diagnosis with nonpsychotic Diagnostic and Statistical Manual (DSM) IV MDD, (3) 24-item Hamilton Rating Scale for Depression (HRSD) score ≥ 16 , (4) willing to and capable of providing informed consent and complying with study procedures. Exclusion criteria are (1) current comorbid Axis I DSM IV disorder other than Nicotine Dependence, Adjustment Disorder, or Anxiety Disorder, (2) diagnosis of substance abuse or dependence (excluding Nicotine Dependence) within the past 12 months, (3) history of psychosis, psychotic disorder, mania, or bipolar disorder, (4) diagnosis of probable Alzheimer's Disease, Vascular Dementia, or Parkinson's Disease, (5) MMSE < 24 , (6) HRSD suicide item > 2 or Clinical Global Impressions (CGI)-Severity88 score of 7 at baseline, (7) history of allergic or adverse reaction to escitalopram and duloxetine, or non-response to adequate trial of escitalopram (at least 4 weeks at dose of 20mg) and duloxetine (at least 4 weeks at dose of 60mg) during the current episode, (8) current treatment with psychotherapy, antidepressants, antipsychotics, or mood stabilizers, (9) having contraindication to MRI scanning (such as metal in body) or unable to tolerate the scanning procedures (i.e., severe obesity, claustrophobia) (for subjects undergoing MRI scanning only), and (10) acute, severe, or unstable medical or neurological illness.

Recruitment Procedures

Describe settings where recruitment will occur

Subjects will be recruited through radio and newspaper advertisements and referrals from other physicians.

How and by whom will subjects be approached and/or recruited?

Individuals presenting to the Adult and Late Life Depression Research Clinic (ALLDRC) are evaluated under IRB #7284R, "Evaluation at the Adult and Late Life Depression Center." Following this evaluation, one of the study psychiatrists authorized to obtain informed consent will discuss study participation with subjects.

How will the study be advertised/publicized?

Newspaper and radio advertisements, flyers posted around CPMC, physician referrals.

Do you have ads/recruitment material requiring review at this time?

Yes

Does this study involve a clinical trial?

Yes

Please provide the NCT Registration Number

NCT01931202

Concurrent Research Studies

Will subjects in this study participate in or be recruited from other studies?

Yes

Describe concurrent research involvement

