7. Regarding DTI, we will acquire the baseline image B0 and the diffusion weighted images (DWI) in 25 directions. To isolate brain from non-brain tissue, we will apply the DTI software in the FSL analytic package (Analysis Group, FMRIB, Oxford, UK) to the B0 image and use the isolated brain as a mask to define the brain in DWIs. The images will be corrected for eddy current distortions, and then we will fit a diffusion tensor model to the DWI data at each voxel. The tensor model yields a voxel-wise map of 1st/2nd/3rd eigenvectors and eigenvalues, fractional anisotropy (FA), and mean diffusivity across the entire brain. The DT images for all participants will be coregistered by applying affine transformation to a template brain using the B0 images, thereby permitting voxel-wise statistical analyses of the various DTI measures. In addition to the whole-brain voxel-wise statistical analyses, we will perform statistical analyses of the mean FA value within specified ROIs defined using regions of WMH in anatomical MR images for each participant. ROIs with significantly differing DTI measures will be associated with specific pathways in the brain by coregistering the template brain to a DTI atlas (LONI ICBM DTI atlas, cmrm.med.jhmi.edu), which parcellates the brain into 23 functionally meaningful anatomical regions, grouped by brainstem, projection fibers, association fibers, and commissural fibers (described in detail at cmrm.med.jhmi.edu). Finally, within the coordinate space of the template brain, we will perform diffusion tensor tractography from regions within prefrontal cortex to striatum and statistically analyze the various DTI measures at each voxel along these pathways. Statistically significant differences in the DTI measures along these pathways would indicate disruption of anatomical connectivity between regions in the prefrontal cortex and the striatum.

Neuropsychological testing

1. The baseline neuropsychological test battery assembled for this study meets five important criteria that we were striving to achieve (see Table 4): 1) it is short and well tolerated by the elderly (total administration time approximately 40 minutes), 2) it is a reasonably comprehensive assessment of executive functioning, 3) the measures are capable of tapping a range of abilities (minimizes floor and ceiling effects), 4) it comprises standard tests, and 5) it allows for reliable administration by trained technicians.

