*Analyses for Exploratory Aim:* As described above, DTI data for each subject will yield a voxel-wise map of FA values across the entire brain. Substituting these FA values for ED/WMH in Model 1, we will assess at each voxel whether the FA values differ significantly by randomized condition on expectancy or antidepressant outcome over time. Although Bonferroni correction could be employed to correct for multiple statistical comparisons, it tends to be overly conservative since the sets of FA correlate with one another. Alternatively, we will use statistical analyses based on the theory of Gaussian random fields (GRFs) defined across the entire brain to account for correlations across voxels and to calculate corrected p-values. In addition to GRF-corrected maps, we will also apply the theory of False Discovery Rate (FDR) to control for multiple comparisons while permitting discovery of 5% false positives. Because the method for FDR permits a specified percent of false positive, the method for FDR is statistically more powerful in detecting significant differences in the brain. Our method also allows us to include the use of covariates such as age, sex, and IQ when calculating corrected P-values. Next, we will identify the neural pathways associated with voxels having significant  $g(t_j) * I_i^{TRT} * FA_i$  interactions by coregistering the template DTI brain to the DTI atlas described above. Finally, we will assess the integrity of the frontostriatal and frontolimbic tracts by performing tractography from PFC regions to striatal and limbic areas and assessing whether the significant voxels lie along the fiber tracts.

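### Affine-only alignment of the DTI images cannot match local brain shape at ages 60 to 90, so voxel FA near fluid can mix tract with fluid and weaken the Exploratory Aim's tract findings

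*Protocol*

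**What the plan says.** **Aim.** The Protocol's Exploratory Aim is "To assess the integrity of frontostriatal and frontolimbic white matter tracts using DTI" and to "explore whether specific damage to these pathways is associated with diminished expectancy effects". The SAP overview says DTI is there to locate white matter damage more precisely.

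**Alignment.** Protocol, Study Procedures, MRI scanning, item 7: every patient's DT images "will be coregistered by applying affine transformation to a template brain using the B0 images". The Protocol presents this step as what makes the voxel-wise analysis possible. Neither document mentions, in the text available to me, a nonlinear step, a white-matter skeleton, a fluid correction or a registration check.

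**Analyses that use the alignment.** Item 7 runs tractography from prefrontal cortex to striatum in template space, tests the DTI measures at each voxel along those pathways, and takes significant differences there as a sign of disrupted connectivity. The SAP (Analyses for Exploratory Aim) adds: "Substituting these FA values for ED/WMH in Model 1, we will assess at each voxel". It then places significant voxels using an atlas matched to the same template, and finishes by "assessing whether the significant voxels lie along the fiber tracts".

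**Analysis less dependent on it.** Item 7 also plans mean FA in ROIs defined from the WMH on each participant's own anatomical images.

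**The concern.** A voxel-wise moderator analysis assumes that a given template voxel holds the same tissue in every patient. A global linear map cannot secure this where local anatomy differs. Beside a fluid space, one patient's voxel may be all tract and another's part tract and part fluid. FA is lower in fluid, so the second patient looks as if the tract were damaged.

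Two things are at stake. The first is power: FA that partly measures alignment error is a noisier moderator, and a real tract effect is harder to find. The second is interpretation. More fluid lowers FA, so if patients with more atrophy show a smaller difference between conditions, the spurious result has the same sign as the tract hypothesis. The plan names no alternative explanation for a significant pathway difference.

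**Working it through.** The plan gives no figure for this step, so there is nothing to reproduce. The check is a reading of the method, followed by an illustration on assumed inputs.

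**1. What the alignment can do.** In three dimensions an affine map has a 3 × 3 matrix and a shift: 9 + 3 = 12 parameters for the whole brain. It can match overall position, size and shear, but not the shape of one ventricle.

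**2. What a template voxel then measures.** Let T be true tract FA, C the FA of fluid and f the fluid fraction of the voxel. By simple mixing (an approximation), observed FA is A = (1 − f)T + fC.

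**3. What this does to the tested term, time × condition × FA.**
- If f is the same in all patients, A is a linear rescaling of T. With f = 0.2 and C = 0.10, A = 0.8T + 0.02. The interaction test is unchanged.
- If f varies between patients but does not modify the effect of condition, it acts mainly as noise and costs power.
- If f varies and atrophy does modify the effect of condition, A can show an interaction even when T plays no part.

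**4. How much of the variance could be fluid.** The documents give no FA or atrophy values, so all inputs are assumptions: T averages 0.45, C = 0.10, f averages 0.2, and T and f are independent. Then

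- tract part = ((1 − 0.2)² + SD(f)²) × SD(T)²
- fluid part = (0.45 − 0.10)² × SD(f)²
- fluid share = fluid part / (fluid part + tract part)

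With SD(T) = 0.05 and SD(f) = 0.10: tract part = (0.64 + 0.01) × 0.0025 = 0.001625; fluid part = 0.1225 × 0.01 = 0.001225; share = 0.001225 / 0.00285 = 43%.

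| SD(T) | SD(f) 0.02 | 0.05 | 0.10 | 0.20 |
|---|---|---|---|---|
| 0.03 | 8% | 35% | 68% | 89% |
| 0.05 | 3% | 16% | 43% | 74% |
| 0.08 | 1% | 7% | 23% | 53% |

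The share is negligible where local alignment is good and dominant where it is poor. The plan has no check that would show which applies.

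**5. Whether age adjustment removes it.** In Model 1 the moderator enters through β4, β6, β7 and β8. Age, as part of X, enters only through β9, with no product with time or condition, so it does not adjust the tested interaction. Suppose age were instead removed from f completely, with an assumed correlation of 0.5. The fluid part would be multiplied by 1 − 0.25 = 0.75. At SD(T) = 0.05 the share falls from 43% to 36% (SD(f) 0.10) and from 74% to 68% (SD(f) 0.20). Even that more generous adjustment leaves most of it.

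**The case against.** Several points on the other side have weight.

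- **Tract analysis.** A reader might infer that tract involvement is judged only from whole-brain significant voxels. It is not: item 7 also tests along prefrontal-striatal pathways. That analysis runs in the same template space, however, and inherits the same alignment.
- **Participant-level ROIs.** These depend less on the template. But they sample lesions rather than the named tracts, and a patient with no visible WMH may have no ROI.
- **Covariates and eligibility.** Age is in Model 1, and the SAP allows age, sex and IQ in the voxel analysis. Step 5 shows the limit of age as a main effect, and no atrophy measure is named. Excluding dementia, Parkinson's disease, MMSE below 24 and severe or unstable neurological illness plausibly narrows the range of atrophy. It does not remove it.
- **Multiplicity control.** Random-field and FDR corrections address the number of tests, not what each voxel contains.
- **Randomization.** Condition is randomized, so contaminated FA does not by itself create a false interaction. This stands, and it is why the misreading is conditional on atrophy being a moderator.
- **Unseen text.** The SAP refers back to sections that were not available to me, and one part of it was removed before review. Fuller preprocessing detail may exist there.

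**Conclusion.** The point holds for the Exploratory Aim, mostly at voxels near fluid. Affine-only alignment blurs true tract effects there. It permits a false tract reading only if atrophy itself moderates the open versus placebo-controlled difference. Aims 1 and 2 rest on the Stroop and the rated WMH score and are untouched.

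The size cannot be computed from the documents. The 1% to 89% range rests wholly on assumed values and shows only that the effect may be trivial or dominant. That ventricular size varies materially in this sample is inferred from the age range. The documents also do not say how much of the named tracts lies near fluid.

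Two stronger readings are not supported:

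- **A large, known bias.** On the same assumed FA values, fluid fractions of 10% to 30% lower FA by 0.10 × 0.35 = 0.035 to 0.30 × 0.35 = 0.105. Divided by an SD of 0.05, that is 0.7 to 2.1 SD. This is a mean shift at a fixed fraction. Step 3 shows that a shift shared by all patients does not bias a moderator; only variation between patients matters.
- **A failed aim.** The aim is to explore, the problem is local, and the comparator is a 0 to 3 visual rating. Reduced precision near fluid is what the text supports.

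**What to change.** **In Protocol item 7:** replace affine-only alignment by affine followed by nonlinear registration, or by projection onto a white-matter skeleton, with a visual check of each registration. The DTI scans and a T1-weighted 3D image are already in the acquisition list (item 5). Settle the method before the DTI-outcome models are run. The Protocol reports that only data analysis is ongoing; if any of these models have already been run, say so.

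**In the interpretation:** qualify the sentence that treats pathway differences as disrupted connectivity. State that residual misalignment and local atrophy are alternative explanations near fluid.

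**Optional:** enter mean FA of the frontostriatal and of the frontolimbic tract into Model 1 as a supplementary analysis, labelled with the date it was added. At this stage it cannot simply be called prespecified.

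**Cost:** computing time, checking of the warps, and a few lines of Protocol and SAP text. No new scans or patients are needed.
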